We have been successful with ChIP assays in both fresh and recently frozen mouse tissues. If a patient consents to fresh tissue collection and the tissue procurement resource contains insufficient sample to release for testing, this testing will not be required. The frozen tissue from the University of Chicago will be sent via FedEx on dry ice the same day to the laboratory of [name] at Roswell Park Cancer Institute [name]. If the surgical sample is harvested on Friday, it will be stored at -70 over the weekend and shipped on Monday morning. In addition, PLA for protein-protein interaction will be performed in [name] laboratory on unstained slides of tumor specimens provided by [name] (Department of Pathology, RPCI). Similarly, PLA will be performed on unstained slides of tumor specimens sent (by FedEx, overnight) from University of Chicago to the laboratory of [name] at RPCI.

Determination of p53 sequence in tumor samples:

All evaluations will be done blindly in the absence of any identifying information from IHC as to the intensity of p53 staining. Various studies have indicated that IHC by itself may not be a reliable method to determine p53 status in tumors. As explained above, IHC determination is based on the assumption that mutant p53 is more stable leading to higher signal in IHC. However, that is not always the case. For example, 20% of tumors with a mutant p53 did not show nuclear accumulation of the protein (2). Sequence determination of p53 gene is more precise in determining wild

type vs. mutant status of p53. Importantly, in studies where DNA sequencing was used to detect p53 mutations, mutant p53 was significantly predictive of resistance to endocrine therapy (1, 2, 47). For reliable status determination, we will analyze sequence of p53 in tumors. All evaluations will be done blindly in the absence of any identifying information from IHC as to the intensity of p53 staining. As a means complimentary to IHC to ascertain the wild type versus mutant status of p53, we will determine the sequence of p53 by next generation sequencing technology with Illumina's MiSeq™ sequencer housed in the Genomics core facility at RPCI. MiSeq™ sequencer is capable of accurate sequence variant detection and has fast turnaround. All steps starting from DNA isolation to data analysis will be performed according to the instructions provided by the manufacturer (Illumina, Inc.). The sequencing will be performed on DNA isolated from tumor tissue (frozen after surgical resection) of patients enrolled to the study at RPCI and University of Chicago. ***This method will provide accurate sequence information even from a heterogeneous tumor sample containing mixture of normal and tumor cells.***

Analysis of p53-target gene transcription:

First, we will analyze if ER α -p53 interaction in tumors affects p53's function as a transcriptional regulator. Toward this goal, we will analyze a selected group of p53-target genes (based on their reported importance in regulating cell cycle and apoptosis (63,64) that are either activated or repressed by p53 in the resected tumor tissue. . ***We have already demonstrated that Survivin (whose transcription is known to be repressed by p53) expression is upregulated as a consequence of ER binding to p53, and treatment with TAM leads to functional activation of p53, thereby restoring p53's ability to repress Survivin expression (65).*** The mRNA levels of these genes will be analyzed by qRT-PCR, a technique routinely used in the PI's laboratory. Subsequently, we will analyze the expression of these genes at the protein level. Immunohistochemistry (IHC) studies of these proteins will be conducted in the core biopsy samples (unstained slides will be requested for biopsies performed outside RPCI) and surgically excised tumor tissue of the study subjects using a tissue microarray (TMA) generated by the Department of Pathology under the supervision of [name]. For patients recruited at the University of Chicago, TMA will be generated at the University of Chicago. IHC will be performed under the direction of the pathologist, with all pathology personnel blinded to treatment assignment. The IHC endpoints will be rounded to the nearest 10% by the pathologist who will be blinded to the treatment group assignment. The ER and p53 status will be determined as described in the earlier section (section 4.1.1). Staining for p21, Bax, puma and Survivin will be evaluated qualitatively and scored on a 0 – 3+ intensity scale (0 = negative staining, 1+ = weak staining, 2+ = moderately intense staining, and 3 + = strong staining. It is to be noted that p53-target gene protein expression will be analyzed by IHC both in the core biopsy samples and surgically excised tumor tissue enabling within-patient comparison of expression profile of these proteins *before* and *after* TAM therapy. Ideally, a similar within-patient approach is desirable for other assays (ChIP and qRT-PCR,) as well. However, it is practically impossible given the limited tissue availability from the pre-surgical biopsy.

VI. STATISTICAL CONSIDERATIONS

The bio-statistician at RPCI will perform the statistical analyses and aid in interpretation of results. Exploratory graphical analysis and data confirmation will precede formal inferential analysis. As this is an investigational study, no correction for multiple testing will be made; p-values less than $\alpha=0.05$ will be deemed statistically significant. While formal power computations are provided, it is expected a larger Phase III trial will be planned to confirm and elaborate promising findings. The demographic and baseline data will be summarized by treatment group. Descriptive statistics such as frequencies and relative frequencies will be computed for all categorical variables. Numeric variables will be summarized using simple descriptive statistics such as mean, standard deviation, quartiles, etc. Ninety-five percent confidence intervals will be computed when appropriate. A variety of graphical techniques will be used to display data.

The primary analyses in Aim 1 are comparisons of ER α -p53 interaction (positive or negative) between independent treatment and control groups. The proportions of patients with positive ChIP assay/PLA will be compared with Fisher's Exact Test, which has 80% power to detect a difference of about 0.41 between the two group; e.g., a difference of 70% in the control group vs. 30% in the TAM group. In Aim 2, mean mRNA levels, as measured by qRT-PCR, will be compared across treatment and control groups. The difference in log fold intensity between treatment and control will be estimated with an independent samples t-confidence interval. The corresponding hypothesis test has

80% power to detect an effect size of 0.91. That is, if the true difference in means is about 0.91 standard deviations, there is an 80% probability our study will correctly reject the null hypothesis of no effect.

Protein expression measured by IHC gives an ordinal variable (0, 1+, 2+, 3+). For each protein, the four-week intensity change ("post – pre" will be between -3 and 3) will be compared between treatment and control groups with the Wilcoxon-Mann-Whitney test. In the control group we expect little change because no treatment has been given between samples. For power calculations we assume 80% of patients in control will have no change and 10% will increase and decrease. As a hypothesis, we estimate half of patients in the treatment group will have no change and the rest will increase one (e.g. from 1+ to 2+) or two categories (e.g. from 1+ to 3+). From simulation we estimate the power to correctly reject the null hypothesis when this alternative is true is about 90%.

It is possible the response variables in Aims 1 and 2 are correlated with clinical factors such as patient age, smoking status, and position in menstrual cycle. Additional exploratory comparisons of response between treatment and control groups will be made after adjustment for clinical factors with linear or logistic regression as appropriate. These secondary analyses may have greater ability to detect a treatment difference by controlling variability unrelated to treatment. PK/PD data modeling was described previously. Pharmacogenomic data will be explored with the general linear model $Y = a + bG + e$, where genotype G is quantified 0, 1, 2 for aa , Aa , AA , respectively; for quantitative response Y , normal linear regression is used; for binary response, logistic regression is used.

Randomization:

Patients will be allocated to treatment or control by block randomization (block size=4). The randomization assignment list will be maintained at RPCI. The nurse/coordinator from University of Chicago will notify the RPCI Network office for a randomization assignment by sending the completed patient registration form to [contact]. The Network Monitor or designee will randomize the patient and send the randomization assignment to the nurse/coordinator at University of Chicago.

Management of Patients After Completion of Tamoxifen Treatment:

Patient would undergo standard of care surgical excision at completion of four week course of tamoxifen. We do not anticipate the four week therapy with tamoxifen to modify the surgical planning including type of breast surgery, sentinel node biopsy or to affect the clinical outcome. After completion of surgical excision they would be recommended routine adjuvant therapy including adjuvant chemotherapy, radiation therapy and at least 5 years of endocrine therapy as dictated by the patient's final stage.

This protocol does not prohibit patients enrolling in any other future investigational studies after completion of surgical excisions.

Dose Modifications And Delays

There will be no dose modification of tamoxifen therapy. The toxicity profile of four weeks of tamoxifen is unknown. In the event of any Grade 2 or higher toxicity during the study attributed to tamoxifen, it will be discontinued and patient will be permanently taken off the study.

VII. NONPROTOCOL THERAPY

Patients should not receive any cancer therapy other than that specified in the protocol or while on Tamoxifen.

Sex Hormonal Therapy

Patients should not receive any sex hormonal therapy such as birth-control pills, hormone replacement therapy or infertility medications while on this protocol.

Radiation Therapy

Patients may not receive any radiation therapy until the completion of the protocol therapy.

Anti-Hormonal therapy

Patients may not receive any hormonal therapy including Aromatase inhibitors or Raloxifene while on the protocol therapy. Patients should be off of these medications for at least 30 days prior to enrollment. They may receive the appropriate adjuvant therapy after surgery.

Alternative therapy

Patient shall not receive any herbal/alternative therapies such as flaxseed or soy products or other medications such as black cohosh.

Non-cancer therapy

Patient may continue all the therapies intended for other than cancer. Patients shall discuss the safety of receiving the concurrent non-cancer medications with the study investigator. If patients are on SSRI's they are not eligible.

VIII. PHARMACEUTICAL INFORMATIONTamoxifen [NSC#180973]

Tamoxifen is supplied in tablet form, each containing 20 mg.

Clinical Safety and Adverse Effects

Adverse effects include hot flashes, nausea (vomiting is rare), vaginal bleeding, discharge or dryness, menstrual irregularities, and skin rash. Other rarely seen adverse effects are hypercalcemia, peripheral edema, leucopenia and transient thrombocytopenia, loss of appetite, distaste for food, pruritus vulvae, depression, dizziness, headache, leg cramps, lightheadedness, confusion, and fatigue. There is a small risk of ovarian cysts occurring. Hair thinning and/or hair loss has also been reported in women taking tamoxifen. Liver cancer and other liver toxicities such as fatty liver, cholestasis, hepatitis and hepatic necrosis have been reported in women taking tamoxifen, though such toxicities rarely can be severe or life-threatening. A few of these serious cases have resulted in death, but whether tamoxifen was the cause of these problems remains uncertain. An increased incidence of cataracts has been noted in rats, although such an increase has not been reported in humans. However, other ophthalmic toxicities, such as corneal scarring or retinal changes, have been reported in a few patients. Tumor flare can appear in patients being treated for metastatic disease. Tamoxifen should not be taken during pregnancy due to potential hazard to the fetus. This includes miscarriage, birth defects, or long-term effects on sexual development (which could be similar to the long-term effects caused by diethylstilbestrol [DES]). Women whose mothers took DES during pregnancy have an increased risk of developing cancer of the vagina or cervix, and may have trouble bearing children. The relevance of findings from animal studies to women who may accidentally take tamoxifen during pregnancy is unknown, but it is essential that effective contraceptive methods be used while taking tamoxifen therapy, and for two months after completing or discontinuing therapy. Tamoxifen may cause changes in the lining of the uterus which could potentially lead to uterine cancer. An early sign of abnormal changes in the uterus may be abnormal vaginal bleeding or pelvic discomfort. An increased risk of uterine cancer has been reported with the use of tamoxifen; however, the level of risk is still uncertain. After an average of 8 years of follow-up, the annual risk observed in a large-scale trial of breast cancer patients taking 20 mg of tamoxifen daily is about 2 per 1,000 women (approximately three times greater than that of a similar group of women in the general population.) Uterine cancer is potentially life-threatening, and some breast cancer patients who developed uterine cancer while taking tamoxifen have subsequently died from that disease. Most of the uterine cancers that have occurred have been diagnosed at an early stage when treatment is highly effective. Tamoxifen may cause changes in the lining of the uterus, such as polyps and hyperplasia, and endometriosis. Data from the NSABP B-14 study show no increase in other (non-uterine) cancers among patients receiving tamoxifen. However, other data suggest a possible increase in second cancers of the gastrointestinal tract among women receiving the drug. Whether an increased risk for other (non-uterine) cancers is associated with tamoxifen is still uncertain and will continue to be evaluated. Women on tamoxifen have an increased risk for developing phlebitis and blood clots. Some studies, but not all, have shown that tamoxifen causes about 1% increase in the incidence of thrombotic events. These include superficial phlebitis, deep vein thrombosis, and pulmonary embolism. Rarely, death has occurred from such events in these studies.

However most of the toxicities reported with Tamoxifen is with long term therapy e.g. 5 years of adjuvant therapy. There are no known or reported toxicity with a short course of tamoxifen such as 14 days.

IX. REPORTING OF ADVERSE DRUG REACTIONS/ DATA AND SAFETY MONITORING PLAN

Investigator Requirements and Responsibilities

The principal investigator (PI) of this study at each site is ultimately responsible for every aspect of the design, conduct, and final analysis of this protocol. Each site PI is responsible to ensure continuous, close monitoring of subjects enrolled on this clinical trial.

Adverse Event Reporting (AER)

Investigators are required by Federal Regulations to report serious adverse events. Investigators are required to notify the Clinical Research Services (CRS), CRS will notify RPCI Institutional Review Board if a patient has a reportable serious adverse event. This study will utilize the **Common Toxicity Criteria version- 3.0** to determine the severity of the adverse event.

Reporting requirements and procedures depend upon:

- (1) whether procedure is suspected of causing the adverse event,
- (2) whether the possibility of such an adverse event was reported in the protocol, consent form, or manufacturer's literature (expected or unexpected adverse event),
- (3) the severity or grade of the adverse event,
- (4) the phase of the study and attribution (the determination of whether an adverse event is related to a medical treatment or procedure). All events in a "reportable" category must be reported.

All serious related and unexpected events must be forwarded to the Roswell Park Cancer Institute Institutional Review Board.

Serious Adverse Events (SAE)

A serious adverse event (SAE) is any experience that suggests a significant hazard, contraindication, side effects or precaution. This includes any experience that:

- Results in death.
- Is a life-threatening adverse drug experience
- Requires inpatient hospitalization or prolongation of existing hospitalization.
- Results in persistent or significant disability/incapacity.
- Is a congenital anomaly/birth defect.
- Requires medical or surgical intervention to prevent one of the outcomes listed above.

Reporting Serious Adverse Events

All SAEs occurring during the course of the study or within 30 days of the last administration of study procedure must be reported to each local IRB per institute policy. At RPCI Clinical Research Services (CRS) must be informed within 24 hours of the knowledge of occurrence (this refers to an AE that meets one or more of the aforementioned serious criteria), Network sites please refer to **appendix 2** as well as following your local IRB policy. The principal investigator or designee will complete and submit an FDA Form 3500A Med Watch for any event that meets the above criteria. Forms will be submitted to the CRS Compliance Office via e-mail to [contact]. Follow-up SAE information must be submitted when information is obtained within 24 hrs.

A final assessment of adverse events will be done thirty days after treatment completion (can be plus or minus 2 days). The well-known side effects of tamoxifen increase with increasing duration of use and increasing age. However, women will be specifically asked about any new onset of shortness of breath, unilateral leg swelling, change in vision, abnormal vaginal bleeding or vasomotor symptoms

Continuing Reviews

Required reporting requirements of adverse events annually at Continuing Reviews will be reported per IRB guidelines. At time of continuing review reporting the principal investigator will be required to report to the IRB the number of patients entered on the trial, the number of patients treated, a summary of all adverse events reported to date using CTC 3.0 grading, a specific list of serious adverse events, and significant literature reporting developments that may affect the safety of participants or the ethics of the study.

The IRB will review annual Data Safety Monitoring Board reports and make recommendations on whether the study should continue unchanged, require modifications/amendment, or be closed based on unacceptable risk to participants.

Symptom diaries

Symptom diaries will not be used to track adverse events.

X. REFERENCES FOR CLINICAL PROTOCOL

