Approximately 60-80% of breast cancers are estrogen receptor alpha (ER α)-positive and estrogen-dependent. The anti-estrogenic drug tamoxifen is an approved treatment for women with both advanced and early stage ER α -positive breast cancer and for prevention of breast cancer in women. However, a large number of patients with ER α -positive breast tumors either do not respond to tamoxifen therapy or develop resistance to it. The mechanisms of such resistance remain largely unclear. ER α promotes proliferation of breast cancer cells, whereas p53 suppresses tumorigenesis by impeding proliferation and/ or promoting apoptosis of cells with genomic damage. Compared to many other cancers, breast cancers do not have high frequency of p53 mutations. In fact, most ER α (+) breast tumors have wild type p53. **Why wild type tumor suppressor protein p53 in such tumors remain functionally inactive has been unclear.** We have recently reported that ER α binds to p53 and represses its function in human breast cancer cells. Our preliminary data show that estrogen enhances the ER α -p53 interaction, whereas tamoxifen and fulvestrant disrupt it. Our findings provide a likely mechanism for the functional repression of wild type p53 in ER α -positive breast cancer. It appears that abrogation of p53 pathway is a major event both in the ER α -positive and ER α -negative tumors; in the former, wild type p53 is functionally repressed by ER α and in the latter case, p53 is inactivated by mutations. Our cellular and molecular data that antiestrogens such as tamoxifen can disrupt ER α -p53 interaction resulting in alleviation of repression of p53 function caused by ER α strongly suggests that disruption of ER α -p53 interaction may explain the clinical observation that breast cancer patients with ER α -positive tumors carrying wild type p53 respond better to tamoxifen therapy as compared to ER α -positive tumors carrying mutant p53. Our observation in retrospective clinical studies is consistent with results from other studies with independent patient cohorts (1, 2).

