This is a multiple institute study coordinated by Roswell Park Cancer Institute Network Office. See Appendix 2 for Network specific information.

Women will present to the University of Chicago Medical Center (UCMC) Breast Center and Roswell Park Cancer Institute (RPCI) breast center with either an abnormal mammogram, new discrete breast mass, or biopsy proven cancer. Those women with abnormal mammograms (BRIRADS 4 and 5) or suspicious masses will undergo a diagnostic core biopsy after being evaluated in the breast center, the intake point of all new breast cases through the surgical clinic. Once an invasive carcinoma is confirmed on core biopsy by our staff pathologist, the majority of women will undergo definitive surgery to remove the tumor and determine staging. Typically, at University of Chicago and RPCI the interval between biopsy and definitive surgery is between two-four weeks. To examine the interaction between ER α and P53 with and without tamoxifen unfixed tumor tissue (fresh or frozen) is needed. A pilot randomized trial is proposed in ER α positive women to study this interaction. ER α positive disease will be identified at their initial visit, or upon return to the clinic to discuss core biopsy results. A p53 staining will be performed on the diagnostic core biopsy if an ER α positive malignancy is identified (Allred score of 3 or higher). The results of the p53 status will not be used for eligibility. ER/PR/HER-2 analysis of the diagnostic core biopsy tissue is done routinely as a standard of care. Women with tumors which are ER α positive will be enrolled if they meet eligibility criteria. Women will either be randomized to standard of care surgical therapy or a four week intervention prior to surgery; Based on our preclinical studies four weeks of tamoxifen exposure is adequate to study the interaction between ER α , p53 and tamoxifen in the tumor tissue. During the intervention, blood will be drawn from the participants to measure levels of tamoxifen metabolites in the blood and test for polymorphisms that may decrease levels of active metabolites. Estradiol and estrone levels in the blood and tumor tissues of all patients with or without intervention will be measured.

Eligibility Criteria:

Inclusion Criteria:

- (a) The patient must consent to be in the study and must have signed an approved consent form conforming to institutional guidelines
- (b) The patient must be 18 years or older.

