- (c) Core biopsy should definitively demonstrate invasive carcinoma.
- (d) Invasive carcinoma should be ER α receptor positive
- (e) The tumor should be approximately at least 1 cm, to account for variability in imaging and imaging occult disease (physical exam, mammography, ultrasound). We recognize that from time to time because of this variation, there might

not be enough tissue available for analysis after surgical excision but this will allow the greatest opportunity to capture as many eligible patients as possible.

- (f) Patients in whom surgical excision of the tumor is part of standard of care management
- (g) ECOG score of 0 or 1
- (h) Negative serum or urine β -hCG pregnancy test at screening for patients of child-bearing potential (this is routinely done if the patient is premenopausal and having surgery)
- (i) Consent to participate in DBBR (RPCI only)

Exclusion Criteria:

- (a) Male patients are not eligible for this study
- (b) Female patients with inoperable tumors or women with stage 4 disease diagnosed on CT, PET, PET/CT or bone scan.
- (c) Patients with diagnosis by FNA cytology only
- (d) Pregnant or lactating women
- (e) Prior therapy for breast cancer, including irradiation, chemo- immuno- and/or hormonal therapy
- (f) Patients receiving any hormonal therapy, e.g. ovarian hormonal replacement therapy, infertility medications etc., are not eligible
- (g) Nonmalignant systemic disease (cardiovascular, renal, hepatic, etc.) that would preclude the patient from being subjected to surgical excision
- (h) Psychiatric or addictive disorders that would preclude obtaining informed consent
- (i) Patients known or suspected to have hypercoagulable syndrome or with history of venous or arterial thrombosis, stroke, TIA, or pulmonary embolism
- (j) Women with non-invasive disease or microinvasion are not eligible.
- (k) Women undergoing neoadjuvant chemotherapy are not eligible
- (l) women currently on tamoxifen and raloxifene for prevention are not eligible
- (m) Patients shall not receive any herbal/alternative therapies such as flaxseed or soy products or black cohosh.
- (n) Patients with a known mutation in p53 (Li Fraumeni Syndrome)

Unevaluable patients are defined as patients who do not have enough tissue for study or who come off early on tamoxifen, and will be replaced on study.

IV. TREATMENT PLAN AND RESEARCH METHODS:

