Standard surgical therapy will be offered to the patient based on the size, location of their tumor or presence of multiple tumors. After the completion of the surgical resection, two core biopsies of the surrounding normal breast tissue will be taken. One will be used to evaluate for tamoxifen and tamoxifen metabolite levels as well as estradiol and estrone levels in the breast tissue. The second will be stored for future pharmacogenomic studies.

Sequential compression devices (SCD's) will be used as part of standard of care for all women undergoing general anesthesia. Even though there is no data to suggest that a short intervention with tamoxifen will increase the risk of thrombosis, only women who get the tamoxifen arm will receive 5000u of subcutaneous heparin in the pre-operative holding area in addition to the use of SCD's for added prophylaxis.

Patients will undergo adjuvant therapy according to the findings of their surgical pathology. If the patient undergoes Oncotype testing as part of their standard of care, we will collect that information as part of our clinical data for analysis.

ENROLLMENT: Patients would be enrolled in this study at both the University of Chicago and the multidisciplinary breast clinic at RPCI. We plan to accrue 50 patients to this study over 9-year study duration. Anticipated rate of accrual would be 2-3 patients a month.

Tamoxifen is commercially available as a 20 mg tablet. The appropriate grant supporting the study will pay for the tamoxifen and will be provided free-of-charge to patients enrolled in this study.

V. REQUIRED STUDIES

Collaborating institutional staff pathologist will supervise all pathology examinations.

Estrogen Receptor, Progesterone Receptor And Her2 Expression Status:

Biopsy specimens: Estrogen and progesterone receptors are critical for inclusion in this protocol and should either be available as a part of routine analysis or will be done as a part of screening for this study in patients otherwise eligible for the study. Enrollment in the study will be predicated on the presence of ER based on an Allred score of 3 or above. The results of the p53 status will not be used for eligibility and will be determined at the end of study. HER2 expression status is not required prior to accrual.

Genotyping:

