PK/PD analysis will be under the supervision of the Director of the Bioanalytics, Metabolomics and Pharmacokinetics (BMPK) Shared Resource facility at RPCI. Two tubes of blood, 10 ml each, will be drawn 0-30 days prior to the first dose of tamoxifen for PK sampling, estradiol and estrone analysis (tube 1), and genotyping (tube 2), and an additional PK sample of one tube at week 2 or 3 after receiving tamoxifen. An additional PK sample will be collected for all patients on the day of surgery. Also, a core tissue biopsy will be collected at the time of surgery to assess the concentration of tamoxifen and its active metabolites, as well as estradiol, in the surrounding breast tissue. Blood drawn prior to tamoxifen administration will be used to calculate the genotype of CYP2D6 and 3A4/5 and also to ensure tamoxifen levels are zero, and to measure the estradiol concentration. The other 2 samples (2 samples in duplicate) will be used to measure plasma and tissue concentrations of both TAM and its metabolites in comparison to estradiol and estrone concentrations by assessing (a) the area under the curve (AUC; $AUC_{\text{tamoxifen}}$, $AUC_{4\text{-OH-tamoxifen}}$, $AUC_{\text{N-desmethyl-tamoxifen}}$, and $AUC_{\text{endoxifen}}$ and the corresponding metabolic ratios), (b) clearance (CL) of TAM ($CL_{\text{tamoxifen}}$), and (c) maximal concentrations (C_{max}) of TAM and its metabolites. With the 2 time points, a population PK model will be built and then used to estimate individual AUCs or CL. With the 2 time points, a population PK model will be built and then used to estimate individual AUCs or CL. These measurements, as well as the observed C_{max} , will then be tested for association with genotype and baseline estradiol concentrations. Demographic and clinical data (ethnicity, current age, age at diagnosis, menopausal status) will be collected for these patients. Samples of blood (10 ml) will be collected in heparinized tubes centrifuged at 4° C and plasma is stored frozen at -70 °C or lower until analysis by LC/MS/MS. Derivation of PK parameters and modeling is described below.

PK/PD Modeling:

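### Estrogen is named as a driver of the ERα-p53 interaction, yet the primary comparisons ignore menopausal status; adjusting for it would be a free gain in precision

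*Combined protocol and SAP*

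**What the plan says.** The summary makes estrogen a driver of the primary endpoint: "Our preliminary data show that estrogen enhances the ER α -p53 interaction, whereas tamoxifen and fulvestrant disrupt it". The background section on ERα and p53 repeats this for estradiol, and the first aim ties the interaction to existing estradiol and estrone levels.

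Eligibility sets no menopausal restriction: "The patient must be 18 years or older". Inclusion criterion (h) plainly expects premenopausal women, saying of the pregnancy test that "this is routinely done if the patient is premenopausal and having surgery".

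Section VI, Randomization, names no stratification factor: "Patients will be allocated to treatment or control by block randomization (block size=4". The primary Aim 1 analysis pools all women: "The proportions of patients with positive ChIP assay/PLA will be compared with Fisher's Exact Test". The Aim 2 mRNA comparison is an independent-samples t interval, also unadjusted.

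Section VI then plans exploratory linear or logistic regressions adjusting for "clinical factors such as patient age, smoking status, and position in menstrual cycle", and remarks that these may detect a treatment difference better. Menopausal status is not on that list. It is collected, however. The PK/PD section says "Demographic and clinical data (ethnicity, current age, age at diagnosis, menopausal status) will be collected for these patients", the baseline history takes last menstrual period and gynecologic history, and the study calendar limits the pregnancy test to premenopausal women.

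**The concern.** If estrogen raises the interaction, pre- and postmenopausal women may differ in positivity before any tamoxifen is given. The planned test treats such a difference as unexplained variation. In a 50-patient trial run once, a chance excess of premenopausal women in one arm would also move the observed arm difference, with no prespecified analysis to account for it.

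The exploratory models do not settle this. They are secondary, their covariate list is open, and one factor they name does not exist for postmenopausal women. No coding rule says how those women would enter a model containing cycle position.

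**Working it through.** **Inputs from the documents.** 50 patients; significance at p < 0.05 without multiplicity correction; 80% power for a difference of about 0.41, for example 70% control v 30% tamoxifen; blocks of 4 with no stratum; unevaluable patients replaced.

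**Assumptions.** 1:1 allocation, so 25 per arm; two-sided testing; premenopausal share s of 25-50%; a pre/post gap g in positivity of 0-40 points, equal in both arms. The documents give neither s nor g.

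**Step 1: reproduce the stated power.** Sum Bin(x; 25, p_C) × Bin(y; 25, p_T) over all outcomes (x, y) with Fisher p ≤ 0.05. This gives 78.2% at 70% v 30% and 80.5% at 70.5% v 29.5%. The 80% detectable difference is 0.408. The plan's figure stands.

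**Step 2: split the rates without changing the overall rates.** For an arm with overall rate p, premenopausal = p + g(1 − s) and postmenopausal = p − g·s. With s = 0.35 and g = 0.30:
- control: 0.70 + 0.195 = 0.895 and 0.70 − 0.105 = 0.595
- tamoxifen: 0.30 + 0.195 = 0.495 and 0.30 − 0.105 = 0.195

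**Step 3: compare the tests.** The alternative is an exact conditional test of a common odds ratio of 1 across two menopausal strata (Mantel-Haenszel type). The null distribution of control-arm positives is the convolution of the two hypergeometric distributions. Allocation is unstratified. With 12,000 simulated trials, the standard error of each power figure is √(0.78 × 0.22 / 12,000) ≈ 0.4 points.

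| Gap | Fisher, s = 35% | Stratified, s = 35% | Gain, s = 25-50% |
|---|---|---|---|
| 0 | 77.9% | 78.6% | about 1 point |
| 10-20 points | – | – | 1-3 points |
| 30 points | 77.9% | 81.9% | 4-5 points |
| 40 points | 78.8% | 85.6% | 5-8 points |

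Fisher power stays at 77-79% in every scenario. The small gain with no gap arises because the stratified exact test is less conservative: with no treatment effect it rejects in 3-4% of trials, against 2.2-2.4% for Fisher (30% premenopausal).

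A second set of runs used odds ratios of 1, 2, 4 and 9 for pre v post (shares of 30% and 50%) and stratified both allocation and test. The gains were 0-1, 1-2, 2-4 and 6-7 points. Stratifying the allocation but keeping Fisher gave 78-81%, so nearly all the gain comes from the analysis.

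**Step 4: chance imbalance.** A 20-point gap between arms in premenopausal share means a difference of 5 or more women out of 25. Its probability is 14.0%, 18.1% and 20.3% at shares of 25%, 35% and 50% when the number of premenopausal women is itself random. It is 22% or 26% (hypergeometric) if exactly 15 or 25 of the 50 are premenopausal; with an odd count a difference of exactly 5 can occur.

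Take 11 premenopausal women on tamoxifen and 6 in control, with the Step 2 rates:
- control expectation: (6 × 0.895 + 19 × 0.595)/25 = 0.667
- tamoxifen expectation: (11 × 0.495 + 14 × 0.195)/25 = 0.327

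The expected difference is 34 points instead of 40. Fisher power for that split is 63%; the stratified test keeps 81%. The mirror-image split has an expected difference of 0.727 − 0.267 = 46 points, so Fisher then overstates the effect.

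No size was calculated for the mRNA comparison.

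**The case against.** **The planned power is not reduced.** This is correct. The 70% and 30% are overall rates, so any pre/post difference is already inside them. A reader might infer that the omission costs the primary test its stated power; Steps 1 and 3 show that it does not.

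**The larger gains need strong assumptions.** Also correct. At s = 35%, a 30-point gap corresponds to odds ratios of about 4-6, and a 40-point gap to 96% v 56% in controls, an odds ratio of about 19. Nothing in the documents says menopausal status tracks estrogen level inside the tumour. One cited reference, judged by its title alone, concerns high tumour estradiol without ovarian function, which would point to a smaller gap.

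**Adjustment is already planned.** In part. A reader might infer that menopausal status is shut out of every analysis. The exploratory list is open and includes age, so it could be added without contradicting the text. It is not prespecified, and the primary comparisons stay unadjusted.

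**Chance imbalance is not bias.** Correct. Averaged over randomizations the Fisher test keeps its type I error. The argument from imbalance concerns how the single realised result is read.

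**Cycle position would exclude postmenopausal women.** A reader might infer this, but the plan states no complete-case rule and no coding. All that can be said is that the handling is unspecified.

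**Estradiol and estrone are measured directly.** The study design section promises both in all patients. However, the treatment plan and study calendar restrict PK/PD blood to the tamoxifen arm, so a baseline value may be missing in controls, and surgery-day values come after randomization. Menopausal status is the more workable covariate.

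**Conclusion.** This is a free improvement, not an error in the plan. The protocol's own rationale points to a baseline factor that the primary analyses leave out and the exploratory list does not name. Under the assumptions above (25 per arm, 70% v 30% overall, the same gap in both arms), using it in an exact stratified test gains about 1 point of power if it does not matter, 1-3 points for a 10-20-point gap, and 4-8 points for a 30-40-point gap. No scenario that was run showed a loss of power or of type I error control. The average gain is modest; steadiness of the one realised result under imbalance is the better reason to act. Both the premenopausal share and the gap are assumptions.

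**What to change.** Before outcome data are examined, amend Section VI:

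- Aim 1: replace the pooled Fisher test with an exact menopause-stratified (Mantel-Haenszel type) test.
- Aim 2 mRNA: add menopausal status as a covariate in the treatment comparison.
- Exploratory models: name menopausal status as a covariate, with cycle position nested within premenopausal women so that postmenopausal women stay in.
- State how menopausal status is defined, and confirm that it is recorded in both arms from baseline information. The sentence on collecting it sits in the PK/PD section.

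Stratified blocks for patients not yet randomized are optional and add little. No change to the IHC comparison is proposed: it already uses within-patient change, and no calculation supports altering it.

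The cost is a few sentences and one stratification variable in a 50-patient trial. The source information is already taken at baseline, so no new assessment is needed.
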